Appendix C – Chronic GVHD activity scoring, and patient-reported outcome measures

cGVHD DATA FORMS
under separate document

i. Study Calendar

Procedure	Screening	Baseline (within 14 days following initiation of steroid therapy for chronic GVHD)	Treatment (+/- 3 days)		Follow Up (+/- 14 days)				Long- term follow up (+/- 28 days)	
			Day 0	Day 14	Month 1	3	6	9		12
										18 and 24 months
Ofatumumab administration										
			X	X						
Screening Procedures										
Eligibility criteria	X									
Informed consent	X									
Efficacy Assessments										
Chronic GVHD activity - NIH score - clinician severity assessments - clinician response assessments - patient- reported severity **		X		X	X	X	X	X	X	X
Patient- reported outcomes - QOL - HAP - Lee symptom scale		X		X	X	X	X	X	X	X
Functional measures - grip strength - 2 minute walk test		X		X	X	X	X	X	X	X
Record systemic immune suppressive		X		X	X	X	X	X	X	X

agents										
Biologic samples		X				X	X		X	
Survival			X	X	X	X	X	X	X	X
Safety Assessments										
Physical exam	X	X	X	X	X	X	X	X	X	X
Karnofsky Performance Status	X	X	X	X	X	X	X	X	X	X
12-lead ECG	X									
CBC, LFT	X	X	X	X	X	X	X	X	X	X
Pregnancy test	X									
Adverse events			X	X	X	X	X	X	X	X

*Enrollment may occur within 14 days of initiation of prednisone for chronic GVHD. Screening tests may occur between start of prednisone and ofatumumab.

*As the MTD will not be known in real-time, patients on any of the phase I dose levels may potentially be those carried forward from the MTD cohort as the recommended phase II dose. Accordingly, patients in all dose levels of the phase I trial will need to have all of the above outlined on-study assessments performed until the MTD is defined. Once the MTD is defined, only those patients in the MTD cohort will continue to have all of the ongoing assessments performed. Conversely, those in the non-MTD cohorts will complete an abbreviated assessment measure set to include only the chronic GVHD activity assessments/response determination and the biologic studies (B cell subsets, BAFF levels) at 6 and 12 month time points. These limited assessments for the non-MTD dose level patients will be included to examine the relationship between dose and clinical response, and dose/pharmacodynamic activity.

**Schirmer test can be done as needed for supportive information in diagnosis of ocular sicca, however is not required by the trial, and does not need to be done on serial visits

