The use of topical agents for control of chronic GVHD manifestations is part of usual clinical care for affected patients. Common examples include various eye drops and artificial tears for ocular sicca, steroid or other immune suppressive agent mouth rinses for oral involvement, or topical steroid creams for mild cutaneous involvement. Use of these agents for patients on study will not be controlled or directed by this protocol. Rather, use of these agents will be directed by treating clinicians as part of usual clinical care. Use of these agents will be recorded in data capture on each study visit. Use of these non-systemic therapies will not inform study endpoints that include requirement for additional systemic immune suppressive therapies.

iv. Supportive antimicrobial prophylaxis on study

- i. All patients on study must receive antimicrobial prophylaxis per BMT guidelines and standards for the prevention of bacterial, viral, fungal, and pneumocystis infections.

V. STUDY OUTCOMES/ANALYSIS ENDPOINTS

1. Safety

a. Definition of DLT for phase I component:

- i. In the phase I study, dose escalation will proceed as previously described. The dose limiting toxicity (DLT) will be defined using CTCAE version 4.0 as the following:
 - Events occurring within 46 days of the last dose of drug (4 half-lives) that are:
 - a) Grade 4 infusion reactions,
 - b) Grade 4 constitutional symptoms at least possibly due to ofatumumab,
 - c) Grade 3 organ toxicities (neurologic, pulmonary, cardiac, gastrointestinal, genitourinary, hepatic, cutaneous) at least possibly due to ofatumumab,
 - d) Grade 4 neutropenia lasting more than 14 days
- ii. Importantly, known infusional toxicities of ofatumumab are managed appropriately with modification of infusion rate or temporary halting of infusion, as well as with supportive care including IV fluids, anti-histamines, and steroids.
- iii. Specifically, grade 1-3 infusion-associated adverse events defined by CTC version 4.0 are not considered DLT in this trial. The occurrence of grade 4 infusion-associated adverse event is considered DLT.
- iv. According to observed toxicities in the phase I component, the greatest dose tolerated in the dose escalation will be carried forward into the phase II component of the trial as the recommended phase II dose.
- v. Events clearly related to chronic GVHD, relapse of the primary hematological disorder, concurrent medication, or infection will not be included as a DLT.

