a. Phase I (those patients in dose levels that are not the MTD to be carried forward into the phase II component)

i. patients will complete 46 days of follow up from last dose of ofatumumab to monitor for DLT

ii. for those not in the MTD cohort, limited data will be collected at 6 and 12 months (clinical response, pharmacodynamics)

b. Phase II (including patients who are carried forward from the phase I component) – patients will complete 24 total months of follow up on study

e. Clarification on duration of follow up and assessments for phase I patients

a. As the MTD will not be known in real-time, patients on any of the phase I dose levels may potentially be those carried forward from the MTD cohort as the recommended phase II dose

b. Accordingly, patients in all dose levels of the phase I trial will need to have all of the above outlined on-study assessments performed until the MTD is defined.

c. Once the MTD is defined, only those patients in the MTD cohort will continue to have all of the ongoing assessments performed

d. Conversely, those in the non-MTD cohorts will complete an abbreviated assessment measure set to include only the chronic GVHD activity assessments/response determination and the biologic studies (B cell

subsets, BAFF levels) at 6 and 12 month time points. These limited assessments for the non-MTD dose level patients will be included to examine the relationship between dose and clinical response, and dose/pharmacodynamic activity.

VI. STATISTICAL ANALYSIS:

Study design and sample size estimation:

In the phase I component, dose escalation procedure is modeled after the data reported for ofatumumab in treatment of rheumatoid arthritis. Here, doses of 300, 700, and 1000mg were delivered on days 0 and 14. As this dose/schedule was well tolerated, led to significant and sustained (up to 48 weeks) depletion of peripheral blood CD19+ B cells, and there was an association between escalating dose and clinical response ([appendix A](#)), this dose/schedule will be adapted to a phase I design in the primary treatment of chronic GVHD.

The study design of the phase I component represents a traditional (3+3) dose escalation design with the following cohorts of ofatumumab in combination with 1mg/kg/day prednisone therapy:

(cohort -1): 100mg days 0 and 14

cohort 1: 300mg days 0 and 14

cohort 2: 700mg days 0 and 14

cohort 3: 1000mg days 0 and 14

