**cohort/dose level -1 (100mg days 0 and 14) will be pursued only if 2/3 patients in cohort 1 (300mg days 0 and 14) experience DLT.*

Phase I trial endpoint:

Safety of escalating dose of ofatumumab in combination with prednisone.

Definition of dose-limiting toxicity (DLT):

Dose-limiting toxicity attributable to ofatumumab within 46 days of initiation of ofatumumab therapy is defined in the *above section V.1 safety for definition of DLT*. The occurrence of DLT attributable to ofatumumab in $\leq 17\%$ serves as the boundary for the maximally tolerated dose (MTD) of ofatumumab.

Phase I trial procedures and analysis:

The initial group of 3 patients will be enrolled in the cohort 1. Dose escalation of ofatumumab will proceed according to the following: If no DLT is observed among 3 patients in a cohort, the next group of 3 will be treated at the next highest dose level. If the current level (i.e., the level at which no DLTs are observed) is the highest dose

level, three additional patients will be enrolled (total of six). If one DLT is observed among 3 patients in a cohort, the next group of 3 will be treated at this same dose level. If no more DLT is observed among the 3 additional patients (i.e. one DLT in total is observed among the 6 patients), then the next 3 patients will be treatment at the next highest dose level. If at least 1 more DLT is observed among the 3 additional patients, then the MTD is exceeded. If 6 patients have been treated at the next lower dose level, it will be considered as the MTD. If not, three additional patients will be enrolled. This escalation approach will then be continued until a dose is identified where at most 1 of 6 patients has a DLT. That dose will be considered to be the MTD. If two DLTs are observed among 3 (or fewer) patients in a cohort, the next group of 3 will be treated at the next lowest dose level. If the current level (i.e. the level at which 2 DLTs are observed) is the lowest dose level (300mg days 0 and 14), then a dose level -1 will be pursued, in which a de-escalated dose of 100mg ofatumumab will be given on days 0 and 14.

The total number treated on the phase I component will depend on the occurrence of dose limiting toxicity (DLT), however the maximal number accrued on the phase I study would approximate 12 to 18 total subjects. GSK reviewed phase I data prior to moving forward with the phase II component.

Phase II component:

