All adverse events should be treated appropriately. Such treatment may include changes in study drug treatment including possible interruption or discontinuation, starting or stopping concomitant treatments, changes in the frequency or nature of assessments, hospitalization, or any other medically required intervention. Once an adverse event is detected, it should be followed until its resolution, and assessment should be made at each visit (or more frequently, if necessary) of any changes in severity, the suspected relationship to the study drug, the interventions required to treat it, and the outcome.

Collection of adverse events – study calendar driven collection schedule:

- All grades (1-5) adverse events will be collected within 24 hours of start of infusion of ofatumumab
- Grades 3-5 adverse events occurring by study day 60 must be collected, excepting those that are directly attributable to chronic GVHD or to relapse of the primary hematologic disorder
- From study day 61 onward, only adverse events deemed related to the investigational agent ofatumumab will be collected

Established post-transplantation complications that are anticipated, and thus will not inform study-related reporting of events attributable to ofatumumab from study day 61 onward:

- i. **Chronic GVHD disease activity** – adverse consequences of chronic GVHD activity itself will not be considered as adverse events. These are described in *appendix B*.
- ii. **Renal or hepatic impairment** related to post-transplant medications or complications – Renal or hepatic impairment temporally associated with known transplant-related insults will not be considered adverse events attributable to ofatumumab. Common examples include worsening in renal function associated with calcineurin inhibitors, volume depletion, or end-organ complications from thrombotic microangiopathy (TMA).
- iii. **Electrolyte abnormalities** related to post-transplant medications – Abnormalities in electrolytes including sodium, potassium, magnesium, calcium, and phosphorus are commonly observed following transplant, and are managed with supplementation. All grade electrolyte abnormalities are not considered adverse events attributable to ofatumumab.
- iv. **Infectious complications** following transplant – Infectious complications are frequent after transplant. Anticipated frequencies of infectious complications are listed in the table below (3.g.iii).

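### The abbreviated schedule for phase I patients outside the MTD cohort conflicts with section VII's six-month liver, hepatitis B and SAE follow-up, mainly for a cohort above the MTD

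*Combined protocol and SAP*

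**What the plan says.** Section V.4.d, on end of study, says of phase I patients whose dose is not carried forward: "patients will complete 46 days of follow up from last dose of ofatumumab to monitor for DLT". It adds limited response and pharmacodynamic data at months 6 and 12. Section V.4.e keeps every phase I patient on the full schedule until the MTD is known, after which "only those patients in the MTD cohort will continue to have all of the ongoing assessments performed". The others, in V.4.e and again in the Study Calendar footnote, "will complete an abbreviated assessment measure set to include only the chronic GVHD activity assessments/response determination and the biologic studies", at months 6 and 12. The calendar lists physical examination, CBC/LFT and adverse events as separate safety rows, outside that set.

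Section VII sets longer minimums and names no cohort as exempt:

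- **Liver monitoring:** liver chemistries to at least 6 months after the last dose, and at each study visit.
- **Hepatitis B Screening:** for HBcAb-positive, DNA-negative patients, monitoring every 2-3 months in follow-up, to 6 months after the last dose.
- **SAE Reporting Procedures:** all SAEs, whatever their cause, for at least 6 months after the last dose or to the end of follow-up, whichever is longer. The one stated exception is the start of another therapy.

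The Adverse Events annual report is to present adverse events by dose level.

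**The concern.** A coordinator who follows the footnote literally would stop scheduled safety checks that section VII still requires. Timing makes this worse for one group. Section VI says of the level below a dose that proved too toxic: "If 6 patients have been treated at the next lower dose level, it will be considered as the MTD". In that case the MTD is fixed immediately, and the cohort treated above it is the first to lose its scheduled visits. At stake are liver tests, HBV DNA where it applies, and the chance to learn of SAEs between day 60 and 6 months after the last dose. There is also a reporting consequence: adverse events shown by dose would cover unequal periods, with lengths set by when the MTD happened to be declared.

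**Working it through.** The plan gives no figure to reproduce here. The check compares clauses and counts days.

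**Inputs**
- Last dose on day 14 (sections IV.ii and VI).
- Stated follow-up of 46 days after the last dose (V.4.d).
- Follow-up visits within plus or minus 14 days (Study Calendar).
- Convention: 1 month = 30.4375 days.
- Assumption: each group of three completes its 60-day window before the next starts, with no delay in accrual. This gives the earliest possible switch; slower accrual after a cohort shortens its shortfall.

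**Step 1: dates**
- End of stated follow-up: 14 + 46 = day 60.
- Six months after the last dose: 14 + 6 × 30.4375 = day 196.6.
- Distance between them: 196.6 − 60 = 136.6 days.
- Month 3 visit: 3 × 30.4375 = day 91.3, window days 77.3 to 105.3.
- Month 6 visit: 6 × 30.4375 = day 182.6, window days 168.6 to 196.6.
- For a patient switched at day 60, time to the next scheduled visit: 168.6 − 60 = 108.6 to 196.6 − 60 = 136.6 days. The longest HBV interval allowed is 3 months, or 91.3 days.

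**Step 2: earliest day on study at which the MTD can be defined**

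| Cohort and path | Day on study | Short of day 196.6 by |
|---|---|---|
| Above the MTD, six already treated one level lower | 60 | 136.6 days |
| Above the MTD, three more needed one level lower | 60 + 60 = 120 | 76.6 days |
| One level below the MTD (two groups of three at the MTD) | 60 + 60 + 60 = 180 | 16.6 days |
| Two levels below the MTD | 4 × 60 = 240 | none |

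Only the first path removes the month 3 visit. In the second, that visit's window has closed by day 105, before the switch. In the third, day 180 already lies inside the month 6 window.

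**Step 3: sensitivity to the DLT window**
Section VI counts the DLT window as 46 days from the start of therapy, while V.1.a counts it from the last dose. With the shorter window, a cohort one level below the MTD reaches at least 3 × 46 = 138 days. It is then up to 196.6 − 138 = 58.6 days short, but still keeps month 3. The day 60 floor for a cohort above the MTD is unchanged, because V.4.d fixes it.

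**Step 4: what is lost in the interval**
- **Liver tests.** Month 6 and month 12 tests are probably still done, because section VII asks for them at each visit and the Appendix B liver score uses bilirubin and enzymes. The exposed test is month 3.
- **HBV DNA.** It is a calendar row for no cohort. The footnote therefore cancels no named test; it removes the visit at which the test would naturally be taken.
- **SAEs.** The duty to report remains, but no contact is scheduled to find them.

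**The case against.** Much of the opposing case stands, and it rules out several stronger readings.

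- **Adverse event review.** The rule "From study day 61 onward, only adverse events deemed related to the investigational agent ofatumumab will be collected" sits under a heading that makes collection calendar-driven, and the footnote is part of the calendar. A reader might infer that losing adverse event review at month 12 breaches section VII. It does not.
- **Blood counts.** A reader might infer that section VII's blood counts are dropped. Section VII has no routine count schedule; a CBC appears only in the liver-event work-up. The retained Appendix B form also records platelets and eosinophils, which implies counts at months 6 and 12.
- **Hepatitis B.** One bullet applies only while the patient remains on study, and testing at routine visits is asked for only where possible. The bullet for HBcAb-positive, DNA-negative patients carries no on-study limit, so that part of the conflict remains for them.
- **The cohort with DLTs.** A reader might infer that it is abandoned. Section VII follows any detected adverse event to resolution, and abnormal liver chemistries until they resolve, stabilize or return to baseline. The gap concerns events not yet detected.
- **DLT endpoint.** A reader might infer that it is under-observed. V.1.a and V.4.d use the same 46 days after the last dose, so it is not.
- **Dose-level reporting.** The annual report asks for a presentation by dose; nothing in the plan requires common windows or a formal comparison. Common windows are a recommendation, made so that the presentation is not misread.
- **Timing.** Section VI says "GSK reviewed phase I data prior to moving forward with the phase II component", and its toxicity stopping rule describes the first six phase II patients as already treated. Extra visits may no longer be possible.

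None of this answers the core point. The liver and SAE minimums have no cohort exemption, and section V.4 gives the affected patients a shorter follow-up.

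**Conclusion.** The conflict is real and of low severity. It bears chiefly on a cohort above the MTD when six patients had already been treated one level lower: the gap is then up to about 137 days short of 6 months after the last dose, with no scheduled visit for 109-137 days. Cohorts below the MTD are short by about 17 days at most under the sequential 60-day assumption, and by about 59 days at most under section VI's shorter window. If 1000 mg became the MTD, no cohort lies above it and the matter is minor.

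A reader might want a count of affected patients. The documents do not support one: they give no DLT rates or accrual pace, and the approximate phase I total of 12 to 18 does not fix how many fall outside the MTD cohort. The sponsor, knowing the escalation path, can say at once whether anyone was affected. The DLT rule, the 6-month response analysis and the sample size are untouched.

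**What to change.** In V.4 and the calendar footnote, state that the abbreviation covers efficacy, patient-reported and functional measures only. State also that section VII liver, HBV and SAE follow-up continues for all treated patients to at least 6 months after the last dose. Add a month 3 LFT and adverse event check for patients above the MTD, and an SAE contact at 6 months after the last dose, because month 6 on study falls 14 days before that point.

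Where adverse events are presented by dose level, use two common windows: to day 60, and to 6 months after the last dose. List later events separately and note what was collected in each cohort. If phase I follow-up has closed, this reporting change is what remains to be done.

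The cost is at most one extra visit and one contact for a few patients, with HBV DNA only for those to whom the rule applies. The reporting change needs no new data.
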